5.2. Pre-Treatment Criteria

5.2.1. Cycle 1, Day 1

Patients should have C1D1 labs that meet inclusion criteria and otherwise be clinically stable per the treating investigator, prior to starting treatment on C1D1. These labs include total bilirubin, creatinine, and ALT/AST (Section 3.1.4).

5.2.2. Subsequent Cycles

Treatment-related AEs meeting DLT criteria should resolve baseline or Grade 1 to proceed to the next cycle (see section 6). Patients may remain on therapy until progression of MDS per IWG revised criteria, or excess/unresolved toxicity as noted below. Therapy is intended to be given consecutively every 28-day cycle without interruption between cycles. Given the nature of MDS and CMML, patients may delay the start of a cycle for up to 28 days for concurrent illness or ongoing toxicity, drug-related or not, that is grade 3 or higher and is felt to prohibit the initiation of therapy according to the treating investigator (see section 6, Management of IP related toxicities

and dose reductions).

Patients should avoid the use of immunosuppressive medication while on study treatment (exceptions are allowed, see section 5.5). If steroids are administered for immune-related AEs during the period on study treatment, patients should be on doses no greater than 10 mg/day prednisone or equivalent prior to the next treatment.

Treatment delays beyond 28 days for toxicity are not permitted and the patient should be discontinued from the study medication. Patients that are deriving clinical benefit but require a treatment delay beyond 28 days for non-toxicity events should be discussed with the principal investigator.

Patients will be assessed for response to therapy after 2 cycles of treatment, via a bone marrow biopsy performed on day 1 of cycle 3 (\pm 3 business day window). The findings of this marrow are not required to proceed to the next cycle but may be used by the treating investigator as clinically indicated. This will be repeated after cycle 4, on cycle 5 day 1 (\pm 3 business day window). A bone marrow assessment and peripheral blood should also be tested at the end of treatment. Any additional marrow assessments are per the treating investigator. The results of these marrows are not required to proceed to the next cycle unless there is a reason to delay per the treating investigator.

5.3. Agent Administration

5.3.1. MBG453

MBG453 100 mg/1 mL and 400 mg/4 mL Liquid in vial. MBG453 100 mg/1 mL Concentrate for solution for infusion is used for intravenous administration from a dose of 12 mg up to a maximal dose of 2400 mg.

Administration:

MBG453 is administered as an intravenous infusion given over 30 minutes, but which may be given over up to 2 hours, if clinically indicated. The maximum administration time is 120 min \pm 10 min.

Shorter infusion times can be applied, since longer infusion times are considered worst-case with regards to potential protein adsorption. The selection of infusion speed within that requirement is in the responsibility of the project-responsible clinician and needs to comply with the specifications given by the infusion pump.

When administration is complete, flush the line with at least 25 mL of 5% dextrose solution to guarantee that all the MBG453 solution for infusion remaining in the infusion line has been administered.

Dosing:

MBG453 will be administered at a dose of 800mg on day 1 of a 28-day cycle.

Drug, Tubing and Filtration:

Only the materials (infusion bags, infusion syringes, infusion lines and in-line filter) specified below should be used for administration of the study medication. The solution for infusion must be infused through a 0.2 micron in-line filter. The infusion sets including the intravenous filter set have to be prepared according to the instructions supplied by the manufacturers.

The infusion set materials listed below are compatible with MBG453. The following materials are accepted to be used in clinical trials for administration of MBG453 Solution for infusion prepared in 5 % dextrose solution (100 mL bags).

Compatible materials of infusion sets components (doses from 40mg to 2400):

- *100 mL 5% Dextrose infusion bag materials in contact with the drug product:* PolyVinyl Chloride (all plasticizers); PolyEthylene
- *Infusion line materials, material in contact with the drug product (maximum length: 300 cm):* PolyVinyl Chloride (all plasticizers); PolyEthylene
- *Infusion filter materials membrane type:* Positively charged Polyamide, Positively charged PolyEtherSulfone, Neutral PolyEtherSulfone

The infusion set (bag, line, and filter) selected for the study should be approved according to local regulation.

Special Equipment:

Infusion pumps are used according to the recommendation given by the supplier and should be suitable to administer MBG453. The combination of bag, line, filter and pump should be tested in advance to ensure that each connection works properly, without any leak.

Hydration:

There is no prespecified hydration recommendation

Observation Period

There should be a period of at least 1 hour after the infusion whereby the patient requires close observation.

Infusion Reactions:

Infusion reactions (typically consisting of flushing, fevers, chills, and less commonly rigors, dyspnea and hypotension) can occur in patients receiving monoclonal antibody therapies. To reduce the risk of infusion-related reactions, MBG453 should be administered by intravenous infusion over at least 30 min and should not be administered as a bolus injection.

Infusion reactions should be treated promptly with medications directed at relief of symptoms, such as antihistamines and antipyretics, and medications and other interventions needed to maintain cardiovascular and pulmonary function. MBG453

infusion should be interrupted for infusion-related reactions of Common Terminology Criteria for Adverse Events (CTCAE) grade 2 or worse.

5.3.2. Other Modality(ies) or Procedures

N/A.

5.4. **Definition of Dose-Limiting Toxicity (DLT)**

This phase II study will include a safety lead-in to ensure there is no excess toxicity in this patient subgroup. The study will collect adverse events during the first cycle (initial 28 days) of treatment for the first 6 patients treated on study to assess for dose-limiting toxicities (DLTs). If more than one of the first six patients enrolled experiences a DLT, enrollment will pause and safety will be assessed for the lower-risk MDS population prior to further enrollment. At that point any further enrollment would depend upon discussions with the sponsor and treating investigators regarding the event, and whether to stop the study or consider amending the protocol to explore lower doses and alternative dose schedules.

DLTs should be possibly, probably, or definitely related to the study drug. The following AEs will be defined as dose-limiting toxicities if considered to be related to MBG453:

Non-hematologic toxicities:

- Grade 3 non-hematologic toxicities unless attributable to persistent MDS or CMML and excluding toxicities secondary to cytopenias (e.g. febrile neutropenia, infection due to MDS-associated neutropenia, bleeding due to thrombocytopenia).
 - The following will *not* be considered DLTs:
 - Grade 3 fatigue, asthenia, fever, anorexia, or constipation.
 - Grade 3 nausea, vomiting or diarrhea not requiring tube feeding, total parenteral nutrition, or requiring or prolonging hospitalization, and that resolve to grade 1 with appropriate treatment within 7 days
 - Grade 3 or 4 tumor lysis syndrome (TLS) if it is successfully managed clinically and resolves within 72 hours without end-organ damage. Grade 4 TLS lasting >72 hours is a DLT.
 - Grade 3 or 4 isolated electrolyte abnormalities that last < 72 hours.
- All Grade 4 non-hematologic toxicities (excluding toxicities attributable to neutropenia and thrombocytopenia due to active MDS or CMML). Conversely, complications of cytopenias including febrile neutropenia, bleeding, and infections, will be considered DLTs in the absence of evidence of active disease, as well as if the baseline for a given cell line (neutrophils, platelets) is above the threshold where such events would be expected due to disease alone.
- CTCAE grade ≥ 3 immune-related adverse events persisting > 7 days after treatment with corticosteroids (if it improves to < grade 3 it is not considered a DLT)
- CTCAE grade ≥ 2 eye pain or reduction of visual acuity that does not respond to topical therapy and does not improve to grade 1 severity within 2 weeks of initiating topical therapy or requiring systemic treatment

- Treatment-related deaths

Hematologic toxicities:

- \geq Grade 3 hematologic toxicities attributed to active MDS will not be considered DLTs, including complications attributed to cytopenias from disease such as infections during neutropenia or bleeding events during thrombocytopenia. As above this does not include such events in the absence of disease or if occurring at a baseline cell count where such events would be expected.
- Grade 4 neutropenia or thrombocytopenia lasting more than 14 days, and associated with a marrow absent features of MDS, is considered a DLT. A bone marrow assessment is recommended if there is suspicion of drug-related cytopenias.
- In the setting of new grade 4 cytopenias thought possibly, probably, or definitely related, and not resolving to grade 3 or better within 14 days, a bone marrow is recommended. If the bone marrow is absent of disease then this would be considered a DLT.

Management and dose modifications associated with the above adverse events are outlined in Section 6.

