The study will collect adverse events during the first 28 days of treatment for the first 6 patients treated on study to assess for dose-limiting toxicities (DLTs). DLTs will be defined as grade 3 or higher non-hematologic toxicities that are possibly, probably, or definitely related to the study drug (see section 5.4 for more detail). Low blood counts will not be considered DLTs; however, in the setting of persistent grade 4 cytopenias thought possibly, probably, or definitely related, and not resolving within 14 days, a bone marrow is recommended. If the bone marrow is absent of disease then this would be considered a DLT. If more than one of the first six patients enrolled experiences a DLT, enrollment will stop and safety will be assessed for this population prior to further enrollment.

Serious adverse events (SAEs) will be monitored; these preliminarily include deaths, life-threatening AEs, hospitalization, birth defects, or important medical events. SAEs should undergo expedited reporting to the IRB/FDA and Novartis, as appropriate. Patients will be followed for

survival up to 12 months after stopping MBG453

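### Section 5.4 misstates its dose-limiting toxicity rule in two places: a baseline-count clause that lacks a 'not', and no rule for immune-related events that improve on steroids, unresolved at grade 4

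*Combined protocol and SAP*

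**What the plan says.** The lead-in rule in section 5.4 is: "If more than one of the first six patients enrolled experiences a DLT, enrollment will pause", after which safety is reviewed before further enrollment. What counts as a DLT is set out in two lists in the same section.

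On complications of cytopenia (febrile neutropenia, infection, bleeding), the non-hematologic list makes them DLTs when there is no active disease, and also when the patient's baseline for that cell line "is above the threshold where such events would be expected due to disease alone". The hematologic list exempts toxicities and complications attributed to active MDS, then limits the exemption. The limit opens with a reference back, "As above this does not include such events in the absence of disease", and then adds a second condition on the patient's count: "or if occurring at a baseline cell count where such events would be expected".

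On immune-related events, three bullets in the non-hematologic list apply:
- grade 3: "Grade 3 non-hematologic toxicities unless attributable to persistent MDS or CMML and excluding toxicities secondary to cytopenias", followed by a list of named exceptions;
- grade 4: "All Grade 4 non-hematologic toxicities", with an exclusion for toxicities due to disease-related cytopenias;
- immune-related, grade 3 or higher: "immune-related adverse events persisting > 7 days after treatment with corticosteroids (if it improves to < grade 3 it is not considered a DLT").

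Section 1.1 (Study Design) gives a short form, "DLTs will be defined as grade 3 or higher non-hematologic toxicities that are possibly, probably, or definitely related to the study drug", and refers to section 5.4 for detail. Section 6 requires a dose modification when an event meeting the DLT criteria occurs in cycle 1, in any patient. The overall PI may agree exceptions case by case.

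**The concern.** A DLT definition should give one answer for one event. Here the hematologic list says that it repeats the non-hematologic rule but states the reverse condition. The immune-related bullet also overlaps the two general bullets, and no sentence says which prevails.

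MBG453 is an immune checkpoint inhibitor, and section 1.1 asks for particular attention to immune-mediated events, so a steroid-responsive immune event is one the lead-in needs to classify cleanly. The label feeds two operative rules: the pause at two or more DLTs in the first six patients, and the cycle 1 dose-modification rule in section 6. Two investigators could label the same event differently, and each could point to text in section 5.4.

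**Working it through.** **The plan's own figures.** Section 13.1 tabulates the probability of no more than one DLT in six. With true rate p this is (1 − p)^6 + 6p(1 − p)^5.

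| p | 0.10 | 0.20 | 0.30 | 0.40 | 0.50 |
|---|---|---|---|---|---|
| Section 13.1 | 0.89 | 0.66 | 0.42 | 0.23 | 0.11 |
| Recomputed | 0.8857 | 0.6554 | 0.4202 | 0.2333 | 0.1094 |

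All five agree. The Simon design also reproduces: type I error 0.0907 (stated 0.09) and power 0.804 (stated 0.80). The table takes the DLT rate as given, and the Simon design concerns response, so the wording of section 5.4 touches neither.

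**Baseline-count clause.** Take a complication of cytopenia judged at least possibly drug-related.

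| Situation | Non-hematologic list | Hematologic list, read literally | Hematologic list with 'not' inserted |
|---|---|---|---|
| No active disease | DLT | Exemption withdrawn | Exemption withdrawn |
| Active MDS, baseline too high for disease to explain the event | DLT | Exemption not withdrawn | Exemption withdrawn |
| Active MDS, baseline low enough that the event is expected | Excluded | Exemption withdrawn | Exemption stands |

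The literal text departs from the first list in rows 2 and 3. Inserting 'not' restores agreement in all three. Both kinds of patient can enrol: section 3.1.1 admits patients with ANC below 500 cells/uL or platelets below 50k/uL, and admits others by different routes.

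**Immune-related events.** Take a related immune event.

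| Event | General bullets | Immune-related bullet |
|---|---|---|
| Grade 3, below grade 3 within 7 days on steroids | DLT | Not a DLT |
| Grade 4, same course | DLT | Not a DLT |
| Grade 3 or 4, still grade 3 or higher beyond 7 days on steroids | DLT | DLT |

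At grade 3, if the general bullet prevailed, the immune-related bullet would have almost no effect, so it is probably meant to govern. That argument does not carry to grade 4, because the bullet keeps a purpose at grade 3 whichever way grade 4 is read. The exception list names two kinds of event that can be exempt at grade 4, tumor lysis syndrome and isolated electrolyte abnormalities; immune-related events are not in it. Section 6 points the other way from an exemption: five of its eight immune tables (GI, renal, pulmonary, hepatic, other) end therapy at grade 4.

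**When the label decides the pause.** Suppose one of the six has a disputed event, and C of the other five have undisputed DLTs. The total is C or C + 1, and the pause needs 2.
- C = 0: total 0 or 1, no pause either way.
- C = 1: total 1 or 2, so the label decides.
- C of 2 or more: pause either way.

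A probability would need the rate of disputed events. For the 26 MDS/AML patients on monotherapy, the documents do not give immune-related events by grade, cycle and steroid response, so no probability is offered.

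**The case against.** The strongest reply is that the intended meaning can be recovered and that little turns on the literal text. Much of that stands.

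- A reader might infer that the reversed clause turns expected infections and bleeds at low counts into DLTs. It does not. It only withdraws an exemption, and the non-hematologic list still excludes toxicities secondary to cytopenias.
- A reader might also infer that all such events at adequate counts escape. The hematologic exemption reaches only events attributed to active disease, and an event at a count too high for disease to explain would not usually be attributed that way. The practical reach is narrow. It is not empty, because an event can be attributed to disease and still be judged possibly drug-related.
- For grade 4, the reply is that the word 'All' is already not absolute, given the named exceptions, and that the immune-related bullet expressly starts at grade 3. That makes an exemption arguable. It does not settle the matter, since the drafters listed the grade 4 exceptions they wanted.
- It is tempting to say that the steroid parenthesis has no deadline. The 7 days stand in the same bullet.
- Section 1.1 does not add a conflict, because it defers to section 5.4.
- A knock-on effect on expedited reporting (section 7.3.5) is conditional at best. That exemption concerns hematologic toxicity, whereas section 5.4 first deals with febrile neutropenia, bleeding and infection under its non-hematologic list.
- The renal and pulmonary tables in section 6, which resume grade 2–3 events at the same dose, sit awkwardly with the cycle 1 modification rule. That is a separate question, and section 6 allows a modification by changing the interval.

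The pause is also a case review rather than closure.

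**Conclusion.** Section 5.4 is wrong as written in one clause and unresolved in another. The baseline-count clause states the reverse of the rule it refers to; the intended meaning is clear and the practical reach is narrow. For immune-related events that improve on steroids, grade 3 is probably settled by reading the specific bullet over the general one, but grade 4 has two opposite answers and no sentence that chooses.

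The size is limited. With one disputed patient, the label decides the pause only when exactly one of the other five has an undisputed DLT. It can also decide whether the cycle 1 dose-modification rule applies, subject to the overall PI's discretion; at grade 4 that matters less, because most immune tables end therapy anyway. The frequency cannot be estimated from the documents. A reader might infer that the lead-in's operating characteristics or the efficacy design are compromised; neither is. This is a minor to should-fix wording correction, worth making because the rule concerns safety and the change costs almost nothing.

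**What to change.** 1. In the hematologic list, change the clause so that the exemption is withdrawn at a baseline cell count where such events would *not* be expected due to disease alone.
2. State that grade 3 immune-related events are judged only by the immune-related bullet: not a DLT if below grade 3 within 7 days of starting corticosteroids. This fits the 7-day steroid rule in the hepatic and other-immune tables of section 6.
3. Have the sponsor state the grade 4 rule. Either grade 4 immune-related events are always DLTs, which is consistent with the five of eight immune tables that end therapy at grade 4, or they are added to the named exceptions with their conditions.

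As a secondary clarification, one sentence in section 6 could say how the cycle 1 modification rule relates to the renal and pulmonary tables.

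The cost is a wording amendment of about three sentences in section 5.4 and, if wanted, one in section 6. It needs no added patients, procedures or recalculation.

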5.5. General Concomitant Medication and Supportive Care Guidelines

MBG453 is a monoclonal antibody and is not metabolized by cytochrome P450 (CYP450) enzymes, or transported by P-glycoprotein (Pgp) or related ABC membrane transporters, and drug-drug interactions are not anticipated. Cytokines produced by activated lymphocytes may impact the levels of Pgp and the activity of CYP450 enzymes. The clinical relevance of MBG453 immune modulation and potential cytokine production that could impact Pgp and CYP450 is unknown; a clinically relevant drug-drug interactions is considered highly unlikely.

Because a primary goal of the study is to evaluate for hematologic responses, growth factors (including G-CSF, GM-CSF, epoetin, darbepoietin, etc) should not be used during the study period. If a patient is deemed by the treating investigator to urgently require growth factor support e.g. G-CSF in the setting of a life-threatening infection, this may be considered but should also be relayed to the overall PI. Such treatments should not be administered chronically, only during the time of acute illness, if indicated.

While the patient is receiving study therapy, they may not receive other investigational drugs or chemotherapy. They also may not receive other approved chemotherapy drugs, with the exception of short duration growth factor support as noted.

Because MBG453 is thought to work in part through activation of the immune system, patients should not receive systemic immunosuppressive medication at doses greater than 10mg/day of prednisone or equivalent, with the following exceptions:

- Prophylactic use for subjects with imaging contrast dye allergy
- Premedication for transfusions or for other infusions, as clinically indicated.

- Replacement-dose steroids (defined as up to 10 mg/day of prednisone or equivalent dose of corticosteroids) in the setting of adrenal insufficiency. Short course “sick doses” are permitted as long as the dose is reduced to 10 mg/day prior to the next treatment.
- Transient exacerbations of chronic inflammatory conditions such as chronic obstructive pulmonary disease (COPD). Steroids must be reduced to 10 mg/day (or lower dose) of prednisone or equivalent dose of corticosteroids prior to the next treatment with MBG453.
- Acute illness e.g. “stress dose” steroids may be administered but should be tapered prior to the next dose of MBG453
- Upon treatment of MBG453 infusion reactions or MBG453-related irAEs, steroids must be reduced to 10 mg/day (or lower dose) of prednisone or equivalent dose of corticosteroids prior to the next treatment with MBG453.

Topical, inhaled, nasal and ophthalmic steroids are allowed.

The use of live vaccines is not allowed through the duration of the study. Inactivated vaccines are allowed.

5.6. Criteria for Taking a Participant Off Protocol Therapy

Duration of therapy will depend on individual response, evidence of disease progression and tolerance. In the absence of treatment delays due to adverse event(s), treatment may continue for until one of the following criteria applies:

- Disease progression
- Intercurrent illness that prevents further administration of treatment
- Unacceptable treatment-related adverse event(s)
- Participant demonstrates an inability or unwillingness to comply with the medication regimen and/or study requirements
- Participant and/or treating investigator decides to withdraw from the protocol therapy
- General or specific changes in the participant's condition render the participant unacceptable for further treatment in the judgment of the treating investigator

Participants will be removed from the protocol therapy when any of these criteria apply. The reason for removal from protocol therapy, and the date the participant was removed, must be documented in the case report form (CRF). Alternative care options will be discussed with the participant. If MBG453 becomes commercially available and reimbursable, patients may choose to transition off protocol therapy to commercial product.

In the event of unusual or life-threatening complications, treating investigators should immediately notify the Overall PI, [name] at [contact] or paged at [contact].

When a participant is removed from protocol therapy and/or is off of the study, the participant's status must be updated in OnCore in accordance with [REGIST-OP-1](#).

